## Randomization

Immediately following phase 1 testing on day 14, participants will be randomized to one of two experimental groups, either a 28-d (live-in), 55% energy deficit phase (DEF) or a 28-d (live-in), 55% energy deficit phase with exogenous testosterone administration (DEF+TEST). A randomization scheme will be determined using a block design (n=60) and age stratification (< 29 years or ≥ 29 years). Randomization will be done by a biostatistician with no direct study affiliation. Prior to the start of the study, the randomization schedule will be given to the pharmacist. The PBRC clinical research pharmacist will have no direct contact with participants. Treatment administration will be performed by a physician assistant, nurse practitioner, or nurse who will not be aware of treatment assignments. Participants and all study personnel will be blinded to treatment group. The code will be kept as a locked electronic file on a secure server by the pharmacist until study completion or there is a need to break the code for safety of the participant.

## Phase 2: 55% Energy Deficit (live-in diet & activity control). Day 15–Day 42

- During the energy deficit phase, participants will live on Pennington Biomedical's inpatient unit in a 24-hour-a-day controlled setting. Once a day, participants will have their vitals (BP, pulse) measured. All meals will be eaten on the unit and monitored. Daily, participants will be weighed. Additionally, a wrist-worn accelerometer will be used throughout phase 2.
- Throughout phase 2, participants will complete supervised exercise sessions 1-4 times per day. Every 2 weeks, participants will undergo submax met carts for each mode of exercise utilized.
- Participants will consume 100 mL/d  $^2\text{H}_2\text{O}$  (i.e., heavy water) from day 15 to 42.
- Participants will be asked to provide a saliva sample on days 15, 19, 23, 27, 31, 35, and 39 to assess body water enrichment.
- Blood draws will occur on days 28 and 42.
- Cognitive testing will be performed on days 15, 20, 22, 27, 29, 34, 36, 40 and 41 over a 1.5-2 hour period each day.
- A DXA scan will be done on days 28 and 39.
- A 1 hour fMRI will be done on days 36, 37, and 38.
- An injection (placebo or testosterone) will be administered on days 15, 21, 28, and 35.
- Eating Inventories (TFEQ, FCI, FCI trait) will be completed on day 42.
- Muscle biopsies will be collected at rest on day 28 and pre, 60 min and 360 min post a 60 min cycle ergometry exercise session on day 42. **Participants will undergo 7 total muscle biopsy procedures during the entire study period (3 on one leg and 4 on the opposite leg, 3 total incisions).**
- Participants will ingest D3-creatine (D3Cr) (60 mg capsule) on day 39 for estimates of muscle mass at the end of phase 2 (urine collections on days 39, 41, 42).
- On day 39, participants will stay in the metabolic chamber and have urine nitrogen and urine creatinine collected for 24 hours.

- Participants will consume 2 g sucralose dissolved in 180 mL water on the morning of study day 39. A 24-hour urine sample collected for nitrogen and creatinine testing will be used to analyze the sugar substitute ingestion.
- Exercise testing for muscular strength (biodex) will be performed on day 41.
- Participants will be asked to provide a stool sample on days 25 and 39 (+72 hours) for gut microbiome analysis.
- Information regarding adverse events will be collected weekly on days 21, 28, 35, and 42.
- Participants will reside in the metabolic ward at PBRC during phase 2, thus the time commitment for this phase is 24 hours per day.
- Upon completion of each week of Phase 2, participants will receive an incentive item to aid in retention and adherence to the study protocol. Incentive items include a towel, water bottle, t-shirt, and gym bag.

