**PRN: As Needed Follow-up Visit**

- After day 42, if the participant's testosterone levels have not returned to normal levels, a blood draw will occur every 90 days until levels have returned to within normal range (testosterone concentration  $\geq$  300 ng/dL).

**Note: If timeline deviations are unavoidable (e.g. equipment issues, participant illness, unforeseen delays, etc.) schedule alterations, that will not affect study outcomes, may be necessary and are at the discretion of study staff.**

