Endocrine, hematological and physiological biomarkers

Fasted blood samples will be collected biweekly on days 0, 14, 28, 42, 56 and EOS. Blood samples will be analyzed for total testosterone, free testosterone, luteinizing hormone (LH), follicle-stimulating hormone (FSH), sex hormone binding globulin (SHBG), insulin-like growth factor-1 (IGF-1), estradiol, insulin, cortisol and a complete blood count with differential (CBC w/diff). In addition, blood samples will be analyzed for amino acids, lipopolysaccharide-binding protein (LBP), and a chem 15 panel on days 0, 14, 42, 56 and EOS. Prostate-specific antigen (PSA) will be assessed on days 14 and 42. Blood samples collected on days 14, 28, and 42 will be collected before the first muscle biopsy procedure. Additional blood will be collected and archived to allow for future analyses. Blood measure collection time points are shown in **Appendix E**. In addition, testosterone measurements will be taken every 90 days (starting from day 42) to assure full recovery (testosterone concentration  $\geq$  300 ng/dL) once the study has been completed.

Experimental physical activity

Physical activity will be controlled and supervised for accuracy starting on day 15 (i.e., start of phase 2). Varied low, moderate, and high intensity (40-85 % of predetermined  $VO_{2\text{peak}}$ ) endurance-type exercise will be performed during the 28-d live-in phase to increase participants' EIEE 50% above the 14-d acclimation period TDEE. Intensity is defined as <40% of HRR for low intensity,  $\geq$  40% and < 60% of HRR for moderate intensity, and  $\geq$  60% and < 90% of HRR for high intensity. Energy expenditure will be achieved by performing at least one, but no more than four, exercise sessions per day, using a variety of endurance-type modalities (outdoor walking, treadmill [walk, run, and load carriage w/weighted vest equal to 20-35% body mass], cycle ergometer, and elliptical). **Exercise intensity will be verified biweekly and adjusted accordingly using an open circuit indirect calorimeter.**

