## **Data and Specimen Management**

Study participants will be assigned unique subject identification (ID) numbers. Study subject ID numbers will be used on all data collection instruments, to include questionnaires, data collection forms, biological specimen tubes, and computer records. A master list linking the participants' names and ID numbers will be kept in a password-protected computer file with access restricted to the PI and study navigator. Biological samples that are moved off-site (including to USARIEM) for analysis will not contain any personally identifiable information and will be labeled with only the unique subject ID numbers. Staff at these sites will not have access to the master list at any time.

Data collection forms will be kept under lock and key, or password-protected if computerized, and under the control of the PI, associate PIs, and project coordinator. Only personnel assigned to the research study by the PI will have access to the data. Hard-copy data records will be stored for a minimum of 3 years and a maximum of 5 years from the time the study is completed and then destroyed.

The PBRC has a fully integrated, campuswide, automated data management system. All data are entered into a Central Database using existing methodology that has been fully validated and undergoes continuous quality assurance by the PBRC Research Computing Core and NORC. Most data are automatically uploaded from the instruments that measure the endpoint. All self-report inventories and questionnaires will be completed in REDCap via surveys. Participants will be asked to complete the survey via laptop, computer, or tablet. Data will be exported from REDCap for analysis. Exercise testing data will be downloaded from the Parvo Medics' TrueOne® 2400 cart directly following each test and reviewed for integrity. All data are backed up daily, and the Research Computing Core at the PBRC oversees all data management.

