- Energy Deficit. There is a small risk of hypoglycemia when starting a diet lower in calories than participants are accustomed to and increasing caloric expenditure via exercise. Regular blood work and monitoring (including vitals) will be completed throughout the phases for safety checks. Prior to inclusion in the trial, all participants are screened to exclude those with medical or mental disorders that are unsuitable for the trial. Additionally, a barriers interview will be completed during screening to further explain study demands, assess barriers to participation, and screen for psychological and behavioral contraindications to the trial. The clinical site physician will review the medical procedures and psychological health of each participant and attest to suitability for inclusion to into the trial. Once enrolled in the trial, study staff with psychological and behavioral expertise will make daily rounds on the unit to assess mental stability and health of the participants. Any participant

displaying undue distress or other negative psychological symptoms as a result of the trial procedures, the PI and MI will assess if continuation in the trial is warranted. An on-call physician is also available after hours and on weekends.

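### All study personnel are declared blinded, but post-randomization testosterone values, which can reveal the arm, are neither masked nor delayed

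*Combined protocol and SAP*

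**What the plan says.** The Randomization section sets the standard: "Participants and all study personnel will be blinded to treatment group". Three safeguards support it. The pharmacist has no contact with participants, the staff who inject do not know the assignment, and "The code will be kept as a locked electronic file on a secure server by the pharmacist until study completion", unless the code must be broken for a participant's safety.

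The subsection on endocrine, hematological and physiological biomarkers (Objective I: Methodology) then sets the sampling: "Fasted blood samples will be collected biweekly on days 0, 14, 28, 42, 56 and EOS". On the analytes it says: "Blood samples will be analyzed for total testosterone, free testosterone, luteinizing hormone (LH), follicle-stimulating hormone (FSH"; the list continues with SHBG, estradiol and a blood count. Appendix E repeats the testosterone days. Days 28 and 42 fall in the treatment phase; day 56 and EOS fall in recovery.

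On data flow, Data and Specimen Management says "All data are entered into a Central Database using existing methodology", adds that most results upload automatically from the instruments, and limits access as follows: "Only personnel assigned to the research study by the PI will have access to the data". The appendix on the research facilities adds that the data team gives investigators study data sets through web-based desktop access.

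On use of the results, the PRN follow-up section schedules a draw every 90 days after day 42 "if the participant's testosterone levels have not returned to normal levels", with 300 ng/dL as the threshold.

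**The concern.** Blinding of all personnel is a stated property of the trial, but the safeguards cover the allocation code and the syringe, not the laboratory result. By design that result should differ by arm. Objective I, hypothesis A, expects the deficit to produce a hypogonadal state, and the section on testosterone and placebo administration says the dose was chosen to keep testosterone in the normal range. Baseline values from days 0 and 14 sit in the same database, so a reader can look at each man's change.

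The people with access also exercise judgement. The PI helps collect data, leads the analysis and, under Data and Specimen Management, can open the list linking names to ID numbers. The PI and the medical investigator decide on continuation when a procedure is missed or refused (Primary Study Endpoint). Exercise mode and intensity are partly at the trainer's discretion (Risks to Subjects, exercise interventions). Strength is tested on days 41, 55 and at EOS, all after the day-28 draw, and depends on maximal effort in front of staff. Outlier handling, transformations and the choice of cognitive sessions for the cumulative analysis are left open in the statistics sections. If the arm is known or guessed, each of these can lean, and the report could not show that it did not.

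**Working it through.** The plan gives no figure for unblinding. Its sample size does not bear on the point: a difference of 0.75 kg, SD 0.75 kg, two-sided alpha 0.05 and power 0.90 reproduce 22 per group (t-test solution 22.02).

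**Step 1. Is there a masking rule?** Setting the sections side by side:
- Blinding covers all study personnel (Randomization).
- Testosterone is measured during and after treatment (biomarker subsection, Appendix E).
- All data enter the central database, and personnel assigned by the PI have access (Data and Specimen Management).
- No section masks these values, delays their release, or sends them to a reviewer outside the blinded team.

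**Step 2. How far apart could the arms be?** Inputs:
- Baseline 530 ng/dL. This is an assumption, borrowed from the starting level of the testosterone-suppression study cited in the Background. Eligibility allows 300-1,000 ng/dL.
- Falls under energy deficit, from the rationale for duration and severity: 16% in a controlled 21-day, 40% deficit; 50-85% in field training.

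DEF level = 530 x (1 - fall):
- 16%: 530 x 0.84 = 445 ng/dL
- 50%: 530 x 0.50 = 265 ng/dL
- 85%: 530 x 0.15 = 80 ng/dL

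**Step 3. How often does one value identify the arm?** Assume two equal groups, normally distributed percent change with a common SD, mean change of zero in DEF+TEST, and a cut midway between the arm means. With d the between-arm difference in percent change, P(correct) = Φ(d / (2 x SD)). The SD is not in the documents; 20 percentage points is assumed, with 15 and 30 as the range.

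| Fall in DEF | SD 15 | SD 20 | SD 30 |
|---|---|---|---|
| 16% | 70% | Φ(0.40) = 66% | 61% |
| 50% | 95% | Φ(1.25) = 89% | 80% |
| 85% | 99.8% | Φ(2.125) = 98% | 92% |

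Chance is 50%.

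**Step 4. Does the follow-up rule force an early look?** Phase 3 lasts at most 42 days, so EOS is at the latest about day 42 + 42 = 84 and EOS+3 about day 87. Counted from day 42, the first 90-day draw falls at about day 42 + 90 = 132. The threshold could therefore be applied after all of a participant's outcomes are in. The plan allows an earlier reading but does not require one.

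**The case against.** Much of the case on the other side stands.

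- **Timing.** Data and Specimen Management lets blood be frozen until it can be analyzed, and no assay turnaround is given. Automatic upload says nothing about when an assay is run, so day-28 values may not be visible before later assessments.
- **Access.** The access sentence is worded as a restriction, and the Confidentiality section limits identifiable clinical records to the PIs and authorized persons. No section says that strength, cognitive or appetite staff can open hormone results. The PI's access is clearer.
- **Outcomes.** Body mass and DXA lean mass are instrument readings. Many cognitive and mood tests are run by computer, inventories are self-completed, and participants receive their laboratory results only when their own participation ends.
- **Size.** At the controlled-trial fall of 16%, a man starting at 530 stays well above 300 ng/dL and one value does little better than chance.

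A reader might go further and infer three things the documents do not support. First, that LH, FSH and blood counts also drive decisions: only testosterone (follow-up draws) and unspecified blood work are so tied. The sentence "Regular blood work and monitoring (including vitals) will be completed throughout the phases for safety checks" sits under the energy-deficit risk, follows a remark on hypoglycemia and names no hormone. Second, that a blood count gives away the arm: a reversible hemoglobin rise is listed as a possible side effect, with no size. Third, that one reading against 300 ng/dL identifies most men: even a 50% fall leaves anyone who started above 600 ng/dL above that line (600 x 0.50 = 300).

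None of this supplies the missing rule. Late assay is permitted, not required, and restricted access still includes people declared blinded.

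**Conclusion.** The point holds in a limited form. The plan declares all study personnel blinded but leaves post-randomization testosterone unmasked in a database that the PI and assigned personnel can use. Those values can reveal the arm; it is not shown that they will. One value identifies the arm in about 66%, 89% or 98% of men at falls of 16%, 50% or 85%, and in 61% to 99.8% across the whole range examined. These figures rest on an assumed SD and an assumed zero mean change in DEF+TEST; the ng/dL levels rest on an assumed baseline.

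The outcomes at risk are mainly strength testing, staff discretion over exercise and continuation, and analysis choices. The body-mass endpoint and the DXA measure behind the sample size are little affected. This is a weakness in protecting the blind, not evidence that it was broken.

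**What to change.** - State in Randomization and in Data and Specimen Management that post-randomization total and free testosterone, LH, FSH, SHBG and estradiol are hidden from outcome assessors, exercise staff, the PI and analysts until database lock. LH, FSH, SHBG and estradiol are included because they belong to the same panel and no in-study decision is tied to them, not because the documents show that they separate the arms.
- Alternatively, run these assays in batch after each participant's EOS visits. Used alone, this protects assessment but not analysis choices, unless analysts' access is also held until lock.
- Have the testosterone recovery check read after EOS+3, which the 90-day interval allows, or by an existing role outside outcome assessment. If the Research Monitor or the DSMB clinician is chosen, write the duty down, because neither section now assigns laboratory review.
- Record who was unblinded, when and why, including any code break for safety.
- Leave blood-count and chemistry safety review with the medical staff as now, and change no clinical rule.

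The cost is a permission setting and slightly later hormone values. Hormone results would also reach the participant's summary sheet later.

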### Power analysis

Relevant data (means  $\pm$  standard deviations) demonstrating the effects of moderate-to-severe energy deficit on lean body mass were used to determine statistical power and sample size. The percentage total body mass loss (2.7 kg) attributed to lean body mass during a 21-d, higher-protein (1.6 g·kg $^{-1}$ ·d $^{-1}$ ), moderate energy deficit was approximately 30% (0.8 kg). However, the proportion of total body mass loss (5.8 kg) attributed to lean body mass in response to a short-term (~7-d), military training-induced, severe energy deficit was approximately 55% (3.1 kg) (unpublished data). Based on these results, and given the proposed study will induce a 55% energy deficit for 28 days in men consuming a higher-protein diet (1.6 g·kg $^{-1}$ ·d $^{-1}$ ), lean body mass will likely account for 40% of the total body mass loss. Maintaining testosterone within normal physiological ranges is expected to attenuate the loss of lean body mass by 25%, such that those assigned to the testosterone group will lose proportionally 30%, the same percentage of lean body mass as demonstrated in our previous study. Based on these estimates, the sample size necessary to determine the estimated differences between treatments is 22 per group. However, based on previous variability in lean body mass loss in response to moderate-to-severe energy deficit, 25 participants per group is a more conservative estimate to allow for detection of treatment effects in the current study. To account for possible attrition (20%), 30 participants will be assigned to each group (60 total participants). To successfully enroll 60 participants, we request the ability to consent up to 240 participants, given only a third of those briefed and consented in past projects, with more lenient study-specific eligibility criteria, were enrolled. **At least 50 participants will complete the intervention and enrollment will stop once 50 participants have completed the study.**

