**Table 2. Power Analysis and Sample Size Justification**

**Hypothesized Effect (mean  $\pm$  SD)**

$\Delta$ Lean body mass following the 28-d intervention, kg	
DEF	$3.0 \pm 0.75$
DEF+TEST	$2.25 \pm 0.75$
Effect Size	1.0
Alpha	0.05
Power	0.90
Sample Size	22 per group
Expected variability	25 per group
20% study attrition	60 participants total
75% eligibility screen failure	240 total consented individuals

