**Enrollment will stop once 50 participants (25 per group) complete the intervention**

## Study Timeline

Individuals who respond to recruitment materials and indicate interest in study participation will be provided with study-specific information. If still interested, potential participants will be asked a series of demographic and health-related questions to assess eligibility via phone/web-based methods (approximately 15 min). Individuals who meet the initial inclusion/exclusion criteria via **self-reported** responses will be invited to attend two screening visits at Pennington Biomedical Research Center (PBRC). Details of each study visit are described below. See Train Schedule in **Appendix A**.

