#### **Phase 3: Ab Libitum Feeding (free-living). Day 43–Return to Body Mass**

- For days 43 (participants will be released after completing the final test on day 43) to EOS, participants will return to PBRC at least weekly to weigh-in.
- While participants will report to PBRC approximately once a week to weigh-in, each participant will be provided a scale to take home for daily weight measurements during this time frame. All measures will be semi-nude (t-shirt, shorts, socks) and performed after an overnight fast. Prior to distribution of the scales, they will be verified via PBRC's scale calibration verification SOP with a 50 lb. standard weight. At each weekly check, the participant will be asked to return the scale for reverification to ensure accurate weight measurements.
- Participants will complete a 3-day food record (2 weekdays, 1 weekend day) one week into phase 3 (days 50 to 56).
- Accelerometers (wrist and waist worn) will be worn on days 43 through EOS.
- A food intake test with VAS and gut hormones will be done on day 43.
- Blood draws will occur on day 56.
- Cognitive testing will be performed on day 54
- A DXA will be done on day 53.
- A 1 hour fMRI will be done on days 55, 56, and 57.
- Exercise testing for muscular strength (biodex) will be performed on day 55.
- On day 53, participants will stay in the metabolic chamber and have urine nitrogen and urine creatinine collected for 24 hours.
- Participants will consume D3-creatine (D3Cr) (60 mg capsule) on day 53 for estimates of muscle mass (urine collected on days 53, 55, 56).
- Time commitment during phase 3 will be about 2-3 hours per day on days 54-57. On day 43, the time commitment will be about 4 hours. On day 53 (whole-room calorimetry day), participants will be at the facility for 24 hours. On the once a week weigh-in, participants will be at the facility for approximately 30 minutes.

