Energy expenditure, substrate oxidation, and nitrogen balance will be measured for a 24-h period in a metabolic chamber on days 11, 39, and 53 (see **Figure 2**). The metabolic chamber stays will begin before breakfast, after completing the DXA scan, (~0800) and end before receiving breakfast the following morning (~0800). Participants will receive the same meals, snacks, and beverages to control for potential differences between menu days. The timing of those meals will be similar to other days of the study, with the exception of the biopsy study days. While in the metabolic chamber, participants will perform the same amount of daily exercise typically performed during acclimation, 28-d deficit and recovery phase. For uniformity, all exercise will be performed on a cycle ergometer. Lights will be turned off at 2230, and the participants will be awakened at 0630. All urine will be collected for measurement of urinary nitrogen and creatinine excretion rates to determine nitrogen balance. Energy expenditure will be calculated by indirect calorimetry corrected for urinary nitrogen excretion and respiratory quotient. Energy expenditure and substrate oxidation will be calculated for the 24-h period and also partitioned between rest, exercise and sleep. Substrate oxidation (carbohydrate, fat, and protein) will be calculated using standard equations.

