### **Objective I: Statistics**

All data analyses will be based on the intention-to-treat principle using SPSS statistical software, unless otherwise noted. Data will be examined quantitatively and graphically for outliers and other artifacts that might have an undue impact on the analyses. Logarithmic or similar transformations will be applied when necessary to insure the validity of statistical procedures. All tests will be two-sided and considered statistically significant at  $p < 0.05$ .

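### The sample size rests on lean-mass change over 28 deficit days, but the last DXA before refeeding comes after 24 of them, so the planned contrast is read early and probably diluted

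*Combined protocol and SAP*

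**What the plan says.** Phase 2 imposes the 55% energy deficit from day 15 to day 42, which is 28 days. In that phase, "A DXA scan will be done on days 28 and 39". The section on determination of body composition gives the full list as days 0, 11, 28, 39, 53 and EOS, six scans in all, and names DXA as the source of lean body mass.

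The section on energy expenditure fixes the time of day for the scans paired with the chamber (days 11, 39 and 53): "The metabolic chamber stays will begin before breakfast, after completing the DXA scan", at about 0800. In phase 3, which begins on day 43 with a test that includes an ad libitum lunch, "A DXA will be done on day 53".

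The Power analysis section and Table 2 base the sample size on "Lean body mass following the 28-d intervention, kg", with 3.0 ± 0.75 for DEF and 2.25 ± 0.75 for DEF+TEST. The reasoning is that lean mass makes up 40% of the mass lost in DEF and 30% in DEF+TEST: "Maintaining testosterone within normal physiological ranges is expected to attenuate the loss of lean body mass by 25" per cent. The result is that "the sample size necessary to determine the estimated differences between treatments is 22 per group", raised to 25 for variability. The line below Table 2 adds: "Enrollment will stop once 50 participants (25 per group) complete the intervention".

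The Primary Study Endpoint section names total body mass, which is weighed daily through phase 2.

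**The concern.** The quantity in the power calculation and the quantity the scanner records cover different lengths of exposure. The 3.0 and 2.25 kg figures are 40% and 30% of the 7.5 kg that Table 1 predicts for days 15 to 42, so they are 28-day figures. On the morning of day 39 only days 15 to 38 are complete. Days 39 to 42 fall after the scan, and the day-53 scan follows about ten days of free eating. No DXA marks the end of the deficit, and no section reconciles the day-39 scan with Table 2.

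The day-11 scan does not make up the difference. Day 11 to day 39 is 28 calendar days, but days 11 to 14 are in energy balance.

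At stake is the lean-mass comparison at the centre of Objective I-A and its hypothesis. The expected contrast at the scan is probably smaller than the one the trial was sized for, so the stated effect size of 1.0 and power of 0.90 may not describe the measurement taken.

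**Working it through.** **Inputs.** Difference 0.75 kg and SD 0.75 kg (Table 2); two-sided 0.05 (Objective I: Statistics: "All tests will be two-sided and considered statistically significant at" p < 0.05); 22 and 25 per group (Power analysis); deficit 2063 kcal/d and loss 7.5 kg (Table 1). Assumed here: 7700 kcal per kg, linear lean loss, and the SD at 24 days. The documents give none of these three.

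**The plan's own figure.** Normal approximation: n = 2 × (1.960 + 1.282)² × (0.75/0.75)² = 21.0, rounded up to 22 per group, which matches Table 2. With the noncentral t, power is 0.90 at 22 per group and 0.93 at 25.

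**Exposure at the scan.** 39 − 15 = 24 complete deficit days; 24/28 = 0.857.

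**Expected loss.**
- 28 days: 2063 × 28 / 7700 = 7.50 kg, which reproduces Table 1 and supports the 7700 figure.
- 24 days: 2063 × 24 / 7700 = 6.43 kg. Lean loss is 0.40 × 6.43 = 2.57 kg vs 0.30 × 6.43 = 1.93 kg, a difference of 0.64 kg, 14% below 0.75.

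A constant daily deficit is the plan's own assumption. In its light-exercise example, expenditure is 3750 − 625 = 3125 kcal and intake 1062 kcal, which again leaves 2063 kcal.

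**Power (two-sample t-test, two-sided 0.05).**

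| Scan | Difference, kg | SD, kg | Standardised effect | 22 per group | 25 per group |
|---|---|---|---|---|---|
| 28 days, as planned | 0.75 | 0.75 | 1.00 | 0.90 | 0.93 |
| Day 39, SD unchanged | 0.64 | 0.75 | 0.86 | 0.79 | 0.84 |
| Day 39, SD × √(24/28) | 0.64 | 0.69 | 0.93 | 0.85 | 0.89 |
| Day 39, SD × 24/28 | 0.64 | 0.64 | 1.00 | 0.90 | 0.93 |
| Day 42 morning (27 days), SD unchanged | 0.72 | 0.75 | 0.96 | 0.88 | 0.92 |

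With the SD unchanged, 90% power at day 39 needs 30 per group.

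**If loss is front-loaded.** As an illustration only, let the group difference approach its plateau exponentially with a half-life of 7 or 14 days. The share of the 28-day difference present after 24 days is (1 − 2^(−24/h)) / (1 − 2^(−28/h)) = 0.97 for h = 7 and 0.93 for h = 14. Power at 25 per group with SD 0.75 is then 0.92 and 0.89. If the testosterone effect builds up late, the shortfall is larger than in the linear case.

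**The case against.** The strongest defence is that day 39 belongs to a deliberate block. DXA, chamber stay and D3-creatine fall together on days 11 and 39, strength testing follows on days 13 and 41, and biopsies on days 14 and 42. The baseline and late-deficit scans thus hold the same place in the sequence, and Table 2's wording could be read as loose shorthand for this end-of-phase block. The matching is real and is a cost of moving the scan. It does not correct Table 2, whose figures come from 28 days of deficit.

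A reader might infer that the lean-mass effect is never measured, or that the trial fails on its main outcome. The documents do not support that. The scan comes after 86% of the deficit and after all four injections (days 15, 21, 28 and 35). The named primary endpoint is body mass.

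A reader might also infer that power certainly falls below plan. That depends on assumptions. The Power analysis section itself cites 3.1 kg of lean loss in about 7 days of severe deficit; the setting differs, but it makes early loss plausible. The planned analysis is a repeated-measures mixed model, so the t-test figures are approximations. In the other direction, an SD that shrinks fully in proportion to the mean is optimistic, because the scanner error (precision of 1 to 3% in the protocol) does not shrink with fewer deficit days.

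D3-creatine urine runs to day 42, but it estimates skeletal muscle mass from a day-39 dose and does not replace DXA lean mass.

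**Conclusion.** The point holds as a mismatch between the sample-size quantity and the scan schedule. The day count and the pre-breakfast timing are plain in the text. The size of the effect is less certain: about 14% dilution under linear loss, less if loss is front-loaded, more if the treatment effect comes late. Under linear loss, power at the planned 25 completers per group lies between 0.84 and 0.93, so the likely harm is moderate. It is still worth correcting, because the stated effect size is an end-of-deficit figure and the remedy is cheap.

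**What to change.** Move the day-39 DXA to the fasted morning of day 42, before the first biopsy. Participants are in house and fasted then, and 27 deficit days are complete, with an expected difference of 0.75 × 27/28 = 0.72 kg. Leave the day-39 chamber stay and D3-creatine dose where they are, and keep six scans. There is no extra radiation or visit. The costs are a busier day 42, a scan no longer on the same morning as the chamber stay, and loss of the match to the day-11 block, since the scan would now follow strength testing. Table 2 should then say that the scan falls after 27 deficit days.

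Day 43 would give all 28 days but is better avoided. That scan would follow three thigh biopsies, a 60-minute cycling session and a test-day meal on day 42, whereas the day-11 baseline precedes every biopsy. The documents do not say how far this would disturb DXA lean mass.

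If the scan stays on day 39, restate Table 2 as the expected 24-day difference (about 0.64 kg) with its power range, and report the result as a 24-day effect. That costs only an edit.
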